## **5.6 Study Completion and Discontinuation**

### **5.6.1 Study completion and post-study treatment**

A patient will be considered to have completed the study when the patient has completed all the assessments in the last visit planned in the protocol (Visit 8, Month 12).

Continuing care should be provided by investigator and/or referring physician based on patient availability for follow-up. This care may include:

- Enrollment in the extension study: Patients who complete the 12 month study will be offered a 12 month extension study where all patients will receive zoledronic acid CZOL446H2337E1.
- Alternative therapy may be prescribed at the discretion of the treating physician at Month 12.

### **5.6.2 Discontinuation of Study Treatment**

Discontinuation of study treatment for a patient occurs when study drug is stopped earlier than the protocol planned duration i.e. before Visit 5, Month 6, and can be initiated by either the patient or the investigator.

The investigator must discontinue study treatment for a given patient if he/she believes that continuation would negatively impact the risk/benefit of trial participation.

Study treatment must be discontinued under the following circumstances:

- Patient's wish
- Pregnancy (see [Section 6.5.5](#) and [Section 7.4](#))
- Use of prohibited treatment as per recommendations in [Section 5.5.8](#)
- Any situation in which study participation might result in a safety risk to the patient
- Emergence of the following adverse events:
  - Osteonecrosis of the jaw
  - Renal failure
  - Any laboratory abnormalities that in the judgment of the investigator, taking into consideration the patient's overall status, prevents the patient from continuing participation in the study

If discontinuation of study treatment occurs, the patient should NOT be considered withdrawn from the study. The patient should return to the clinic as soon as possible, after discontinuation of study drug, for a study treatment discontinuation visit. Treatment discontinuation visit assessments detailed in Visit 8, Month 12 in [Table 6-1](#) should be completed and recorded in the CRF. The investigator must determine the primary reason for the patient's premature discontinuation of study treatment and record this information on the Dosage administration record CRF.

After study treatment discontinuation, at a minimum, in abbreviated visits, the following data should to be collected at clinic visits or via telephone visits:

- new / concomitant treatments
- adverse events/serious adverse events

If the patient cannot or is unwilling to attend any visit(s), the site staff should maintain regular telephone contact with the patient, or with a person pre-designated by the patient, preferably according to the study visit schedule.

The investigator must contact the IRT to register the patient's discontinuation from study treatment.

If study drug discontinuation occurs because treatment code has been broken, please refer to [Section 5.5.9](#)

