#### **Protocol procedures: blood draws and radiology**

The number of blood draws and frequency of hospital visits in this protocol is within the usual limit of clinical practice for children with these serious underlying diseases. The radiation exposure is increased over routine clinical practice, but within the limits for children who have suffered a fracture and no greater than the exposure during a transatlantic flight. Repeat blood draws and X-rays/DXA will only be requested when absolutely necessary i.e. safety, baseline or end-of-study visits.

In summary, the risks to the children and adolescents in this trial will be minimized by compliance with the eligibility criteria and study procedures, particularly adequate hydration at the time of the infusion, adherence to a diet rich in calcium and vitamin D, regular renal monitoring and contraception in girls of child bearing potential. A maximum dose of 5 mg zoledronic acid (regardless of patient weight) and a minimum 30 minute infusion time 6-monthly are designed to reduce the risk of possible adverse effects. This dose regimen has been used in children with primary and secondary osteoporosis and has shown a favorable risk-benefit profile.

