**Table 6-1 Assessment schedule**

Period	Screen	Treatment						
Visit	1 	2	3	4 T	5	6	7 T	8 and TD and/or PSW
Day	-28	1 	10	90	180	190	270	365
Month				3	6		9	12
Obtain parental informed consent (D) and assent (S)	x							
Medical history (D)	x	x						
Inclusion/exclusion criteria (S)	x	x						
Prior/concomitant medication, including GC (D)	x	x	x	x	x	x	x	x
Physical Exam (S) 	x	x			x			x
Vital signs (D) 	x	x			x			x
Weight (D)	x	x			x			x
Tanner Staging (D), if applicable		x			x			x
Blood and urine for central laboratory analysis 	x	(x)	x		x	x		x
Pregnancy test, if applicable 	x	x		x 	x			x
Serum 25 (OH) vitamin D	x							x
Ionized calcium (local lab) (D) 		x						
Serum creatinine (local lab) (D) 	x	x						
Biomarkers (serum P1NP, NTX, BSAP, TRAP-5b)		x			x			x
Urine collection for PK (D) 								x
Pain assessment (D) 		x		x	x		x	x
DXA measurements 	x				x			x
X-ray 	x							x
AE/SAE(D) 	x	x	x	x	x	x	x	x
Dispense calcium and vitamin D, if required	x	x			x			x
Contact IRT	x	x			x			x

Period	Screen	Treatment															
Visit	1	2	3	4T	5	6	7T	8 and TD and/or PSW									
Day	-28	1	10	90	180	190	270	365									
i.v. drug administration (ZOL/placebo) (D)		x			x												
Study Completion form (D)								x									

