
1 V1 lab results, including GFR should be available prior to V2
 
2 All randomized patients will have limited blood chemistry assessments, GFR & urinalysis performed at Visit 3 (10 days after Visit 2) and Visit 6 (10 days after Visit 5). An optional repeat at V2 is included, if the time between screening and V2 is close to 4 weeks.
 
3 Test to be performed for females with childbearing potential only. Serum test for central laboratory at screening and final visits, local urine test prior to infusion at Visits 2 and 5 – if positive, infusion should not be started.
 
4 Screening DXA and X-rays should be performed at Visit 1 to ensure the central imaging laboratory can provide status on patient eligibility; these assessments should be performed early in the screening process.
 
5 Ionized Ca measured pre-dose (local lab) only before the first infusion, if below normal range, treat and repeat test before study drug infusion, if visit needs to be re-scheduled inform the monitor.
 
6 Lumbar spine, total body and [REDACTED]
 
7 Lateral thoracolumbar spine and posteroanterior (PA) left hand/wrist (for bone-age assessment and cortical bone thickness)
 
8 Including an oral examination for exposed bone. At screening visit the PI will perform an oral exam and , if needed, will refer the patient to a dentist
 
9 For exclusion purposes if increase between Visits 1 and 2 greater than 0.5 mg/dL (44.2 µmol/L).
 
10 Pain is assessed using Faces Pain Scale-Revised (FPS-R)
 
11 An AP (anteroposterior) spine X-ray will be employed at screening, in order to identify fractures that may not be readily visualized on the lateral spine because of rotation/scoliosis/other
 
[12 Only sites where additional safeguards required: Supervised urine pregnancy test]
 
 	
 
15 SAEs only to be collected from signing informed consent
 
16 Pulse rate and blood pressure only
 
17 Urine collection for PK: either an overnight sample, or collected over at least 4-hours during the day, for details, see Lab Manual
 
18 Screening visit can be on different days to permit scheduling of all investigations during the 28-day screening period
 
T = Telephone visit, S = Source documentation, D = Database, GC = Glucocorticoid, TD = study treatment discontinuation, PSW = Premature patient withdrawal
																	

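### After a stop for pregnancy, the protocol as written calls for the Visit 8 spine X-ray and DXA, and no section says otherwise

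*Protocol*

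**What the plan says.** Protocol Section 5.6.2 lists the circumstances in which study treatment must be stopped, and pregnancy is one of them. The section makes clear that a patient who stops drug stays in the study. It then gives one instruction for all stops, whatever the reason: "The patient should return to the clinic as soon as possible, after discontinuation of study drug, for a study treatment discontinuation visit". The content of that visit is set by reference: "Treatment discontinuation visit assessments detailed in Visit 8, Month 12 in" Table 6-1 should be completed and entered in the CRF.

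In Table 6-1, the final visit, treatment discontinuation and premature withdrawal share one column, headed "8 and TD and/or PSW". Both the DXA row and the X-ray row are marked in it. Footnote 6 gives the DXA sites as lumbar spine, total body and a redacted item. Footnote 7 defines the X-ray as "Lateral thoracolumbar spine and posteroanterior (PA) left hand/wrist". Section 6.4.1 confirms the lateral spine film at the final visit.

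The opening text of Section 6 adds a rule for patients who leave the study early for any reason: every final-visit assessment will be performed.

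On a positive pregnancy test before an infusion, Table 6-1 footnote 3 says "if positive, infusion should not be started". Section 6.5.5 covers the timing of tests and, at sites with additional safeguards, contact with the investigator. Section 7.4 covers contraception, reporting and follow-up of the outcome.

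**The concern.** The protocol plans for pregnancy as a foreseeable event. It enrols girls up to age 17, requires contraception where applicable, tests before each infusion and at the final visit, and adds a Visit 4 test in some countries. These provisions guard a pregnancy against the study drug. None of them deals with the study's own imaging.

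Because the discontinuation visit borrows the Visit 8 column wholesale, a site that follows the text takes a girl stopped for pregnancy to a lumbar spine X-ray and DXA done for research measurement. The stake is radiation exposure of a pregnant minor through a default that seems not to have been considered. A secondary stake is inconsistency: sites would each have to decide what to omit, and the missing values that result would not be foreseen in the plan.

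**Working it through.** No calculation decides this point. The check is to follow the text from the stop to the images and look for an exception at each step.

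1. **Trigger.** Section 5.6.2: pregnancy is on the mandatory stop list.
2. **Visit.** Section 5.6.2: a discontinuation visit follows promptly, with no distinction by reason for stopping.
3. **Content.** Section 5.6.2 points to Visit 8 of Table 6-1, and the shared column marks DXA and X-ray.
4. **Footnotes on those rows.** DXA carries footnotes 4 and 6; X-ray carries 4, 7 and 11. Footnote 4 concerns screening, 6 the DXA sites, 7 the X-ray views and 11 a screening AP film. None concerns pregnancy. Some footnotes of the table are blacked out, but neither imaging row refers to them, so redaction does not explain the gap.
5. **Pregnancy sections.** Section 6.5.5 covers testing. Section 7.4 covers risk information, contraception, reporting and outcome. Neither mentions imaging.
6. **Positive test.** Footnote 3 acts on the infusion only.

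Two related routes reach the same images:

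- A girl who leaves the study altogether falls under Section 6, whose wording is firmer (will, where 5.6.2 has should).
- Section 5.6.2 defines treatment discontinuation as stopping before Visit 5, Month 6. A girl found pregnant later remains in the study and meets the same DXA and X-ray at the scheduled Visit 8, again with no exception.

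Order within a visit is also open. At Visit 5 the urine test is placed before the infusion, and DXA is marked at the same visit with no order stated between test and scan. At Visit 8 a serum sample goes to the central laboratory, and nothing says whether its result comes before the imaging.

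The consequence for the primary analysis can be traced too. Protocol Section 9.1.2 and the SAP admit a patient to the MITT population for the primary endpoint only with a baseline and a post-baseline lumbar spine value. Protocol Section 9.4.3 and the SAP carry the last value forward to Month 12. The SAP uses CRF visits without windows. For a girl stopped before Month 6:

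- with a discontinuation DXA, she can enter the MITT population and her value can be carried forward;
- without one, and with no later scan, she does not meet the MITT definition. The zero-change rule in 9.4.3 cannot bring her back, because it operates within that population.

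The plan randomizes about 92 patients to obtain 82 evaluable, so it already allows for 92 − 82 = 10 losses. One missing patient is 1/82 = 1.2% of the evaluable target.

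**The case against.** The best reply is that silence is not an instruction. The 5.6.2 wording is should, so the protocol calls for the imaging and does not strictly compel it. Telephone contact is allowed when a patient cannot or will not attend. Section 11.1 expects investigators to act at once for a patient's safety even where that departs from the protocol. The DXA and X-ray manuals, the Imaging Charter and the consent form are not available here and might contain an exception.

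Much of this stands as mitigation, and few investigators would image without thought. It does not close the gap. The telephone provision is not tied to pregnancy, Section 11.1 leaves the matter to each investigator, and the protocol cites no exception in the manuals.

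Several stronger readings are tempting, and the documents do not support them:

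- *A contradiction with Section 3.6.* The sentence "Repeat blood draws and X-rays/DXA will only be requested when absolutely necessary" limits repeat procedures only, and it goes on to allow end-of-study visits. It does not address pregnancy.
- *Imaging of no analytic use.* As traced above, a discontinuation DXA can settle MITT membership and supply the carried-forward value.
- *A second DXA after a positive test at Visit 5.* Nothing requires one if that visit serves as the discontinuation visit. It is also unclear whether a stop at Visit 5 meets the 5.6.2 definition, which refers to stopping before that visit.
- *An obligatory deviation record for sites that omit the images.* No passage says so.

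**Conclusion.** The point holds as a gap between sections. Followed as written, 5.6.2 and Table 6-1 lead from a mandatory stop for pregnancy to research spine radiography and DXA, and no section sets this aside. It is more than a missing detail, because a stated rule produces the result.

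Its size cannot be given as a count: the documents state no expected pregnancies, and no figure should be attached. The event is probably rare in a trial of about 92 children, but that is an assumption. The weight lies in the consequence for each affected participant. The effect on the primary comparison should be small, since a single loss sits well inside the planned allowance.

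The conclusion assumes that no exception exists in the imaging manuals, Imaging Charter or consent form.

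**What to change.** Reconcile Section 5.6.2, the opening of Section 6, Table 6-1 (including footnote 3), Section 6.5.5 and Section 7.4 so that they agree on three things:

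- the imaging rows do not apply automatically, through the shared column, after a stop for pregnancy;
- the protocol states which study assessments apply to such a patient, both at discontinuation and for a pregnancy found after Month 6;
- the order of pregnancy test and study imaging is stated for visits that have both (Visits 5 and 8).

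The clinical content of these statements is for the sponsor and investigator to decide. If an imaging manual already deals with the matter, the protocol should refer to it.

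In drafting terms this is a table footnote and a sentence or two. The cost is that an affected patient's post-baseline lumbar spine value may be missing, which can remove her from the MITT population or change the value carried forward.

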### **5.6.3 Withdrawal of informed consent**

Patients may voluntarily withdraw consent to participate in the study for any reason at any time. Withdrawal of consent from the study is defined as when a patient:

- Does not want to participate in the study anymore
- and
- Does not want any further visits or assessments
- and
- Does not want any further study related contacts
- and
- Does not allow analysis of already obtained biologic material

In this situation, the investigator must make every effort (e.g. telephone, e-mail, letter) to determine the primary reason for the patient's decision to withdraw his/her consent and record this information in the source document.

Study treatment must be discontinued and no further assessments conducted, and the data that would have been collected at subsequent visits will be considered missing.

Further attempts to contact the patient are not allowed unless safety findings require communicating or follow-up.

All efforts should be made to complete the assessments prior to study withdrawal. A final evaluation at the time of the patient's study withdrawal should be made as detailed in [Table 6-1](#).

#### **5.6.4 Loss to follow-up**

For patients whose status is unclear because they fail to appear for study visits without stating an intention to discontinue or withdraw, the investigator should show "due diligence" by documenting in the source documents steps taken to contact the patient, e.g. dates of telephone calls, registered letters, etc. A patient cannot be considered as lost to follow-up until the time point of his/her scheduled end of study visit has passed.

#### **5.6.5 Early study termination by the sponsor**

The study can be terminated by Novartis at any time for any reason. This may include reasons related to the benefit risk assessment of participating in the study, practical reasons, or for regulatory or medical reasons (including slow enrolment). Should this be necessary, the patient must be seen as soon as possible and treated as a prematurely withdrawn patient. The investigator may be informed of additional procedures to be followed in order to ensure that adequate consideration is given to the protection of the patient's interests. The investigator will be responsible for informing the Institutional Review Board/Independent Ethics Committee (IRBs/IECs) of the early termination of the trial.

## **6 Visit schedule and assessments**

[Table 6-1](#) lists all of the assessments and indicates with an "x" when the visits are performed.

Patients must be seen for all visits on the designated day, or as close to it as possible. Missed or rescheduled visits should not lead to automatic discontinuation. Patients who prematurely discontinue the study for any reason should be scheduled for a visit as soon as possible, at which time all of the assessments listed for the final visit will be performed. At this final visit, all dispensed investigational product should be reconciled and the adverse event and concomitant medications reconciled on the CRF.

**Table 6-1 Assessment schedule**

Period	Screen	Treatment						
Visit	1 	2	3	4 T	5	6	7 T	8 and TD and/or PSW
Day	-28	1 	10	90	180	190	270	365
Month				3	6		9	12
Obtain parental informed consent (D) and assent (S)	x							
Medical history (D)	x	x						
Inclusion/exclusion criteria (S)	x	x						
Prior/concomitant medication, including GC (D)	x	x	x	x	x	x	x	x
Physical Exam (S) 	x	x			x			x
Vital signs (D) 	x	x			x			x
Weight (D)	x	x			x			x
Tanner Staging (D), if applicable		x			x			x
Blood and urine for central laboratory analysis 	x	(x)	x		x	x		x
Pregnancy test, if applicable 	x	x		x 	x			x
Serum 25 (OH) vitamin D	x							x
Ionized calcium (local lab) (D) 		x						
Serum creatinine (local lab) (D) 	x	x						
Biomarkers (serum P1NP, NTX, BSAP, TRAP-5b)		x			x			x
Urine collection for PK (D) 								x
Pain assessment (D) 		x		x	x		x	x
DXA measurements 	x				x			x
X-ray 	x							x
AE/SAE(D) 	x	x	x	x	x	x	x	x
Dispense calcium and vitamin D, if required	x	x			x			x
Contact IRT	x	x			x			x

Period	Screen	Treatment															
Visit	1	2	3	4T	5	6	7T	8 and TD and/or PSW									
Day	-28	1	10	90	180	190	270	365									
i.v. drug administration (ZOL/placebo) (D)		x			x												
Study Completion form (D)								x									

1 V1 lab results, including GFR should be available prior to V2
 
2 All randomized patients will have limited blood chemistry assessments, GFR & urinalysis performed at Visit 3 (10 days after Visit 2) and Visit 6 (10 days after Visit 5). An optional repeat at V2 is included, if the time between screening and V2 is close to 4 weeks.
 
3 Test to be performed for females with childbearing potential only. Serum test for central laboratory at screening and final visits, local urine test prior to infusion at Visits 2 and 5 – if positive, infusion should not be started.
 
4 Screening DXA and X-rays should be performed at Visit 1 to ensure the central imaging laboratory can provide status on patient eligibility; these assessments should be performed early in the screening process.
 
5 Ionized Ca measured pre-dose (local lab) only before the first infusion, if below normal range, treat and repeat test before study drug infusion, if visit needs to be re-scheduled inform the monitor.
 
6 Lumbar spine, total body and [REDACTED]
 
7 Lateral thoracolumbar spine and posteroanterior (PA) left hand/wrist (for bone-age assessment and cortical bone thickness)
 
8 Including an oral examination for exposed bone. At screening visit the PI will perform an oral exam and , if needed, will refer the patient to a dentist
 
9 For exclusion purposes if increase between Visits 1 and 2 greater than 0.5 mg/dL (44.2 µmol/L).
 
10 Pain is assessed using Faces Pain Scale-Revised (FPS-R)
 
11 An AP (anteroposterior) spine X-ray will be employed at screening, in order to identify fractures that may not be readily visualized on the lateral spine because of rotation/scoliosis/other
 
[12 Only sites where additional safeguards required: Supervised urine pregnancy test]
 
 	
 
15 SAEs only to be collected from signing informed consent
 
16 Pulse rate and blood pressure only
 
17 Urine collection for PK: either an overnight sample, or collected over at least 4-hours during the day, for details, see Lab Manual
 
18 Screening visit can be on different days to permit scheduling of all investigations during the 28-day screening period
 
T = Telephone visit, S = Source documentation, D = Database, GC = Glucocorticoid, TD = study treatment discontinuation, PSW = Premature patient withdrawal
																	

## 6.1 Information to be collected on screening failures

All patients who have signed informed consent but are not randomized will have the study completion page for the screening visit, demographics, inclusion/exclusion, and serious adverse event (SAE) data collected. Adverse events that are not SAEs will be followed by the investigator and collected only in the source data.

Should the reason for non-eligibility change at a later clinic appointment e.g. treatment of vitamin D deficiency, deterioration in LS-BMD Z-score or worsening of fracture & etc., the child may be considered for re-screening, subject to medical approval from Novartis – see IRT guide and CRF completion guidelines for further details.

## 6.2 Patient demographics/other baseline characteristics

At the Screening visit, information on age, sex, race, and source of the referral will be collected. Relevant Medical History/Current medical conditions will be recorded and updated at Screening (Visit 1) and at Baseline (Visit 2), prior to the first dose of study medication. The time between Visit 1 and Visit 2 should be as close to 28 days as possible and must not extend beyond 8 weeks. Background information collected at Screening and/or Baseline will include:

- Details of current or past glucocorticoid therapy in the preceding 12 months prior to screening, including dose with start and stop dates
- Current and past concomitant medication
- Disease (chronic rheumatologic conditions, IBD, DMD, and others) related background/historical information
- Other medical history and current medical conditions
- Trauma history, including history of falls
- Previous fracture history
- Tanner Pubertal Staging ([Appendix 2](#))
- Vital signs and physical exams, including oral exam
- Pain assessment
- [REDACTED]
- [REDACTED]

Assessments collected at Screening will include:

1. AP and Lateral Thoraco-Lumbar X-ray to show evidence of vertebral fracture
2. Radiological films and radiological reports for suspected clinical fractures (as previously described in the inclusion criteria).
3. Posteroanterior left hand/wrist X-ray for bone-age and cortical bone thickness evaluation
4. DXA measurements
5. Central laboratory tests
6. Local laboratory test (serum creatinine)

